3. INTRODUCTION

This SAP covers the statistical analysis and reporting for the protocol APVO101-903 Amendment 2.0 dated 29 Jul 2020, and electronic case report form (eCRF) production version of 23 Sep 2019.

4. STUDY OBJECTIVES

4.1 PRIMARY OBJECTIVES

The following are the primary objectives of APVO101-903:

- To evaluate safety of APVO101 in pediatric subjects with hemophilia B for at least 50 ED;
- To assess efficacy of APVO101 prophylaxis with respect to prevention of breakthrough bleeding and with respect to control of hemorrhaging in pediatric subjects with hemophilia B for at least 50 ED;
- To evaluate PK of APVO101 in pediatric subjects with hemophilia B;
- To evaluate APVO101 immunogenicity response (development of inhibitory and non-inhibitory factor IX binding antibodies and antibodies to Chinese hamster ovary cell proteins [CHOP]).

4.2 EXPLORATORY OBJECTIVES

- To evaluate markers of thrombogenicity [D-dimer, thrombin-antithrombin III complex (TAT) and fragment 1+2 (F1+2)] during the first 24 hours post-infusion of APVO101;
- To evaluate efficacy of APVO101 for perioperative management in pediatric subjects with hemophilia B.

5. STUDY DESCRIPTION

5.1 STUDY DESIGN AND TREATMENT

Study APVO101-903 is a Phase 3/4, single arm, open-label clinical trial. The purpose of the study is to evaluate PK, safety, and efficacy of APVO101 prophylaxis in severe or moderately severe hemophilia B subjects <12 years of age. The study is designed to gather information in 2 age groups of previously treated (with a minimum of 50 previous ED to factor IX replacement therapy) pediatric subjects, specifically those <6 years of age and 6-12 years of age.

Study APVO101-903 consists of 3 distinct phases:

- PK Phase
- Treatment Phase (from first dose after PK phase and up to 50 ED visit)
- Continuation Phase (starting from first dose after 50 ED visit)

Up to 22 subjects will be enrolled in order to have 15 and 20 evaluable subjects to complete the study (i.e., completion of PK assessments and a minimum of 50 ED visit). Treatment with APVO101 to support a surgical procedure (if required) is permitted for subjects in Treatment/Continuation phases of the study.

5.1.1 PK PHASE

PK evaluation will consist of administration of a single 75 ± 5 IU/kg dose, followed by factor IX activity and safety assessments up to 50 hours post-infusion. Dose will be administered after a 4-day washout period from previous factor IX replacement therapy or 3 half-lives washout of a factor IX product with a prolonged half-life.

5.1.2 TREATMENT PHASE

After completion of PK Phase assessments, subjects will be treated with a prophylaxis regimen of APVO101. Subjects will receive a single intravenous (IV) dose of APVO101 twice weekly or at a frequency of infusions as determined appropriate by the investigator for the particular study subject for a total of 50 ED (approximately 6 months). The starting prophylaxis dose will be based on APVO101 recovery from PK Phase assessments (only pre-infusion and 15-30 minute post-infusion samples; ideally within the recommended dose range: 35 – 75 IU/kg, twice weekly).

For treatment and control of breakthrough, spontaneous or trauma-related bleeding episodes, the dose should be based on severity of bleeding episodes; see below:

- Minor bleeding episodes and/or moderate bleeding episodes: 40 – 60 IU/kg;
- Major or life-threatening bleeding episodes: 60 – 100 IU/kg.

During APVO101 prophylaxis treatment and/or APVO101 treatment for control and management of bleeding episodes, every effort will be made to ensure that the prescribed dose per kilogram body weight is given. However, since it may be difficult to determine fractions of a vial for purposes of providing an exact dose, it is acceptable to round up or down to the nearest vial. The process of rounding up or down should not, however, result in the study subject receiving $>120\%$ or $<90\%$ of the prescribed dose. The exact amount of factor IX infused must be recorded.

5.1.3 CONTINUATION PHASE

Following completion of the Treatment Phase (i.e., 50 ED), the investigator will assess the subject's dose and either assign the most recent dose from Treatment Phase or modify the dose if clinically indicated for an additional ≥ 50 ED. The Continuation Phase dose should be within the recommended dose range of 35 – 75 IU/kg, twice weekly.

For treatment and control of breakthrough, spontaneous or trauma-related bleeding episodes,

the dose should be based on severity of bleeding episodes; see below:

- Minor and/or moderate bleeding episodes: 40 – 60 IU/kg
- Major or life-threatening bleeding episodes: 60 – 100 IU/kg

5.1.4 SURGERY

In the event of a minor or major surgery during the course of study participation (Treatment/Continuation Phases), use of either bolus or continuous infusion of APVO101 for surgical coverage is permissible.

Examples of major surgical procedures include synovectomy, knee or hip replacement, total tooth extraction, tonsillectomy and/or adenoidectomy, surgery for intracranial hemorrhage, radial head excision, arthrodesis, ankle surgery, abdominal surgery, herniorrhaphy, or surgery for major muscle bleed management.

The following dosing is recommended for major surgical procedures:

- If using bolus infusions, an infusion of up to 120 IU/kg will be given within 1 hour prior to the start of the procedure, followed by an infusion of approximately 60 IU/kg 12 hours after the first infusion, and up to 120 IU/kg 24 hours after the first infusion, depending on the subject's post-infusion factor IX activity. This regimen of bolus infusions will continue every 12 hours as long as the physician and surgeon deem necessary, but for a minimum of 3 days post-procedure for major surgery or a minimum of 1 day post-procedure for minor surgery.
- If administering a continuous infusion, it will also continue for a minimum of 3 days post-procedure for major surgery or a minimum of 1 day post-procedure for minor surgery. The infusion rate, dose and timing of subsequent infusions and adjustments in dosing will be recorded and guided by factor IX assay results, with the doses of APVO101 administered appropriately to ensure that the plasma factor IX level does not drop below 60%. If continuous infusion is used, the plasma level of factor IX should range between 70% and 110%.

5.2 SAFETY MONITORING COMMITTEE

A Safety Monitoring Committee (SMC) will provide ongoing review of safety data during the trial. Following study initiation, the SMC will meet as needed to review ongoing safety data. The SMC will be responsible for assessing safety and monitoring overall conduct and integrity of the trial. In fulfilling these responsibilities, the SMC may make recommendations concerning continuation and/or stopping of the trial as it relates to safety and risk to the subject population.

6. RANDOMIZATION AND BLINDING

The study is an open-label single-arm study; subjects and members of the clinical study team will not be blinded to treatment.

7. SAMPLE SIZE AND POWER CALCULATION

No formal sample size calculation was performed given that all planned analyses are descriptive in nature. Up to 22 subjects will be enrolled to ensure that at least 15 to 20 evaluable subjects complete the study (i.e., completion of PK assessments and a minimum of 50 ED). The target sample size is intended to enhance the existing pediatric sample size to be compliant with the European Medicines Agency regulatory guidelines and the Food and Drug Administration post-

marketing requirement for APVO101.

8. ANALYSIS ENDPOINTS

8.1 PK ENDPOINTS

PK data will be listed. Detailed descriptions of all PK analyses are provided in a separate PK SAP. Analysis will be included in a separate report.

8.2 EFFICACY ENDPOINTS

8.2.1 PRIMARY EFFICACY ENDPOINT:

ABR while on prophylaxis to prevent bleeding episodes.

8.2.2 SECONDARY EFFICACY ENDPOINTS:

Bleeding episode level:

- Subject rating of efficacy;
- Change in pain;
- Change in swelling;
- Time from onset of bleeding to the first infusion;
- Time from onset of treatment until resolution of the bleeding episode;
- Number of infusions required to treat the bleeding episode.

Subject level:

- Investigator rating of APVO101 prophylaxis efficacy;
- Investigator rating of APVO101 efficacy for control and management of bleeding episodes.

8.2.3 EXPLORATORY EFFICACY ENDPOINTS:

- Surgeon assessment of estimated blood loss at time of surgery
- Surgeon assessment of post-surgery blood loss (at 12-hour and 24-hour post-surgery time points).

8.3 SAFETY ENDPOINTS

- AEs
- Inhibitory factor IX antibodies
- Non-inhibitory factor IX antibodies
- Anti-CHOP antibodies
- Thrombogenicity markers

9. ANALYSIS POPULATIONS

Screened population: All screened subjects.

Safety population: All subjects who received at least one dose of the study drug. This population will be used for all safety and efficacy analyses.

PK population: All subjects who have a valid PK assessment. A PK assessment will be considered valid if quantifiable and evaluable concentration is available.

10. ANALYTICAL PLAN AND STATISTICAL METHODS

10.1 GENERAL CONVENTIONS AND STATISTICAL CONSIDERATIONS

All statistical analyses will be performed and data appendices will be created using the SAS system version 9.4 or higher.

Data collected in this study will be presented in summary tables and subject data listings. Unless otherwise specified, all data will be summarized overall and by age group (<6 years and 6 to <12 years).

Subjects in the younger age group must remain < 6 years age throughout the treatment period (at least 50 ED) and the upper age group must remain < 12 years throughout the treatment period (at least 50 ED).

Descriptive statistics (number of non-missing values, mean, standard deviation [SD], median, first quartile [Q1], third quartile [Q3], minimum and maximum) will be presented for continuous variables. The number of decimal places in mean, median and quartiles will be equal to number of decimal places in the data + 1, decimal places in standard deviation = decimal places in the data + 2, number of decimal places in minimum/maximum will be equal to number of decimal places in the data.

Frequency distributions (counts and percentages) will be presented for categorical variables. If not specified otherwise, the number of observations with non-missing values will be the denominator for percentage calculation. Percentages will include one decimal place except for 100% where no decimal places will be provided.

By-visit and by-study phase summaries will be presented using nominal eCRF visits (which can be up to ± 5 ED to actual exposure days, see section 15)

All data collected will be presented in the data listings. Missing parts of the partial dates will be represented with dashes in the listings.

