6.4. Continuation Phase Assessments

Treatment with APVO101 beyond 50 ED (accumulated during the Treatment Phase) will constitute Continuation Phase treatment.

Following 50 ED visit, subjects will be assessed at 75 ED (± 5 ED), 100 ED (± 5 ED) and every 3 months (~ 25 ED ± 5 ED) thereafter until end of study (*note: subjects may continue on study until last-subject-in completes 100 ED visit*) for the following:

1. Physical exam, vital signs, body weight and height
2. Concomitant medications
3. Local laboratory assessments:
 - a. Serum chemistry (for patients below 17 kg, collect if blood volumes allow)
 - b. Complete blood count (CBC) with differential (for patients below 17 kg, collect if blood volumes allow)
 - c. Urinalysis [urine dipstick, followed by microscopy if abnormal]
4. Central laboratory assessments:
 - a. Inhibitory factor IX antibodies (Nijmegen modified Bethesda assay)
 - b. Non-inhibitory factor IX binding antibodies
 - c. Anti-CHOP antibodies
5. Review of subject diary: infusions, bleeding summary, subject's efficacy assessment, adverse events, concomitant medications and compliance
6. Assessment of adverse events
7. Investigator's assessment of efficacy
8. Assessment of major and target joints (100 ED only)

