Compliance % = $100\% [\text{number of infusions recorded in the subject diary} / (A + B)]$, where $A = [2 * (\text{date of last dose when patient was on 'twice weekly' frequency} - \text{date of first dose})] / 7$

$B = (\text{date of last dose when patient was on 'once weekly' frequency} - \text{date of first dose when patient was on 'once weekly' frequency}) / 7$

If patient dose-frequency was changed more than once, compliance will be calculated similar to the above but taking into account all periods of different dose frequencies in the denominator.

The following **measures of exposure** will be presented for the study:

Parameter	Description
Exposure Day (ED)	APVO101 exposure/infusion. ED will be calculated as the total number of APVO101 infusions during all phases of the study: Pharmacokinetic (PK) [1], Treatment, and Continuation phases, including surgery if applicable. If a subject receives more than one infusion in a single day, all infusions on that day will count as one ED.
Average Exposure per exposure day (IU)	Average APVO101 dose (IU): Sum of all dosages received by a subject (excluding PK doses and dosing during surgery), divided by number of exposure days (excluding PK and surgery)
Average Exposure per exposure day (IU/kg)	Similar to above but for dose in IU/kg
Total Exposure (IU) – PK phase	Planned PK dose IU [2]
Total Exposure (IU/kg) – PK phase	Planned PK dose IU/kg [2]
Total Exposure (IU) –	N/A, no surgeries in the study at the moment of the Statistical Analysis

Surgeries	Plan (SAP) update [3]
Total Exposure (IU/kg) – Surgeries	N/A, no surgeries in the study at the moment of the SAP update [3]
Total Exposure (IU) – All Phases combined including surgeries	Sum of all doses (IU) during the study (PK [1], Treatment and Continuation phases, including surgery if applicable).
Total Exposure (IU/kg) – All Phases combined including surgeries	Similar above but for dose in (IU/kg)

[1] including additional PK during Treatment/Continuation phases

[2] PK during Treatment/Continuation phases should not be included

[3] if surgeries occur in the study by the time of database lock, exposure during surgeries will be derived similar to other total exposure parameters, i.e., as sum of all doses in IU or IU/kg associated with surgery.

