10.7.1 ANALYSIS OF PRIMARY EFFICACY ENDPOINT

The number of bleeding episodes and the number of months observed will be determined from the subject diary. The months of observation will be calculated from the first date of the Treatment Phase to the last prophylaxis entry into the subject diary.

ABR while on prophylaxis to prevent bleeding episodes will be calculated and summarized using median, Q1, Q3 and 95% exact confidence interval for the mean, assuming that the rates follow a Poisson distribution.

ABR overall = (number of bleeding episodes starting from first dose after PK Phase up to 3 days after the last dose of APVO101 given for prophylaxis)/[(treatment end date +3 – treatment start date+1)/365.25]. If a subject left the study earlier than 3 days after last dose, date of end of study will be taken instead of (treatment end date +3 days).

ABR Treatment Phase = (number of bleeding episodes starting from first dose after PK Phase up to 3 days after the last dose of APVO101 given for prophylaxis up to 50 ED)/[(last dose ≤50ED +3 – treatment start date +1)/365.25]. In case first dose after 50 ED occurred earlier than 3 days after 50 ED then this dose date – 1 should be taken as reference end date. If a subject left the study earlier than 3 days after last dose in treatment phase, date of end of study will be taken instead of (last dose ≤50 ED + 3 days).

ABR Continuation Phase = (number of bleeding episodes starting from first dose after 50 ED up to 3 days after last dose of APVO101 given for prophylaxis)/[(treatment end date +3 – first dose after 50 ED+1)/365.25]. If a subject left the study earlier than 3 days after last dose, date of end of study will be taken instead of (treatment end date +3 days).

Note: a bleeding episode which occurred after PK dose but prior to completion of PK assessment will be included into ABR calculations.

In addition, analysis of ABR will be repeated on the normalized data (square-root transformation will be used to normalize ABR).

Number of subjects with at least one bleeding episode and no bleeding episodes will also be summarized.

The analysis of ABR will be repeated for Spontaneous ABR which will consider only spontaneous bleeding episodes in the numerator. Denominator will remain the same as for ABR. Spontaneous ABR for Treatment, Continuation phases as well as overall will be derived.

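### The Treatment and Continuation windows for phase-specific ABR can overlap by a day or leave days out, and two unreconciled rules place the boundary between them

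*SAP*

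**What the plan says.** **Visit-based split.** SAP 5.1 defines the phases as "Treatment Phase (from first dose after PK phase and up to 50 ED visit" and "Continuation Phase (starting from first dose after 50 ED visit". SAP 10.1 repeats the idea for reporting: "By-visit and by-study phase summaries will be presented using nominal eCRF visits", and it notes that these visits can lie as much as 5 ED from the actual count.

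**Count-based split.** SAP 10.7.1 drops the word visit. Its Treatment Phase denominator is built from "last dose ≤50ED +3 – treatment start date +1", and its Continuation Phase starts, inclusively, on the first dose after 50 ED. One cut-back is given: "In case first dose after 50 ED occurred earlier than 3 days after 50 ED then this dose date" minus one day becomes the end date. Overall ABR has its own start-to-end formula with no internal boundary. Spontaneous ABR uses the same denominators as ABR.

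**Secondary endpoints.** SAP 10.7.2 uses the same three-day tail for the Treatment Phase but does not repeat the cut-back. It starts Continuation at the first post-50 ED dose given for prophylaxis, a restriction that the 10.7.1 start does not carry.

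**What counts as an ED.** Among the exposure measures in SAP 2, "ED will be calculated as the total number of APVO101 infusions during all phases of the study", and the PK dose is included. Protocol 6.4 says: "Treatment with APVO101 beyond 50 ED (accumulated during the Treatment Phase) will constitute Continuation Phase treatment".

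**The concern.** A phase breakdown should place each day of follow-up, and each bleed, in exactly one phase. Here the Treatment end date and the Continuation start date are set separately, and the cut-back linking them covers only some dosing gaps. Before that question arises, the SAP gives two ways to locate the boundary.

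The stake is the reproducibility and internal consistency of the phase tables. Two programmers could follow the SAP faithfully and report different Treatment and Continuation ABRs, and bleeds summed over the two phases need not equal the overall count. With 15 to 20 evaluable children and few bleeds expected, one misplaced bleed shows.

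**Working it through.** **1. Do the 10.7.1 windows partition time?**

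Let S be the treatment start date, L the last dose at or before 50 ED, N the first dose after 50 ED, E the last prophylaxis dose, and g = N − L. As written:

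- Treatment end = N − 1 if N < L + 3, otherwise L + 3
- Treatment days T = Treatment end − S + 1
- Continuation days C = E + 3 − N + 1
- Overall days O = E + 3 − S + 1

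So T + C − O = Treatment end − N + 1. This is 0 for g = 1 or 2, and 4 − g for g ≥ 3.

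| Gap g (days) | Treatment ends | Continuation starts | T + C − O |
|---|---|---|---|
| 1 | L | L + 1 | 0 |
| 2 | L + 1 | L + 2 | 0 |
| 3 | L + 3 | L + 3 | +1 (day N in both) |
| 4 | L + 3 | L + 4 | 0 |
| 5 | L + 3 | L + 5 | −1 |
| 7 | L + 3 | L + 7 | −3 (days in neither) |
| 14 | L + 3 | L + 14 | −10 |

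In 10.7.2 there is no cut-back, so 4 − g applies at every gap: gaps of 1 and 2 days also overlap, by 3 and 2 days.

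*Example, g = 3.* Start on day 0, alternate 4- and 3-day gaps, 100 doses: L = day 172, N = day 175, E = day 347. T = 176, C = 350 − 175 + 1 = 176, O = 351; T + C = 352. One bleed on day 175 gives 365.25/176 = 2.08 in each phase and 365.25/351 = 1.04 overall. It is one bleed, counted twice across the phases.

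*Example, once weekly.* L = day 343, N = day 350, E = day 700. T = 347, C = 354, O = 704; T + C = 701. A bleed in the three omitted days gives 0 in both phases and 365.25/704 = 0.52 overall.

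These gaps are ordinary. Twice-weekly dosing on fixed weekdays would give 3- and 4-day gaps (my assumption; the documents say only twice weekly, or another frequency chosen by the investigator). About half of boundary gaps would then be 3 days. SAP 2 expressly foresees once-weekly dosing.

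**2. How far apart are the two boundary rules?**

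At a mean gap of 3.5 days, 50 treatment doses give a window of 49 × 3.5 + 3 + 1 = 175.5 days. A visit 5 ED away moves the boundary by 5 × 3.5 = 17.5 days, and 17.5/175.5 = 10.0%. Counting the PK dose as the first ED gives 48 × 3.5 + 4 = 172 days, 2.0% shorter.

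**3. How many bleeds are exposed?**

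The earlier median ABRs in Protocol 1.2.2 are 0.3 (IB1001-02) and 1.52 (IB1001-01, prophylaxis). Using them as an assumed range of rates:

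- Zone from 45 to 55 ED (35 days), 20 children: 20 × 0.3 × 35/365.25 = 0.6 bleeds to 20 × 1.52 × 35/365.25 = 2.9 bleeds.
- Shared day, 10 children: 10 × 0.3/365.25 = 0.01 to 10 × 1.52/365.25 = 0.04 bleeds, if bleeds are unrelated to dosing days. The figure would be higher if the first dose after 50 ED is itself given for a bleed that day, which 10.7.1 does not rule out.

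**The case against.** The strongest reply is that 10.7.1 governs. It gives explicit formulas, 10.1 is a set of general conventions, and 5.1 describes the design, so a programmer would normally follow the formula. That is a sensible reading, but the SAP does not state it: the proviso in 10.1 allowing exceptions is attached to the age-group sentence, not to the phase sentence. Reading 50 ED as shorthand for the 50 ED visit is also reasonable, and it gives the other answer. Neither reading repairs the tail.

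The reply on the PK dose has more force. The SAP's ED definition sits among measures for the exposure tables, and the SAP does not say that it sets the phase boundary. This is a point to clarify rather than a proven contradiction, and it is worth one dose.

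It is also fair that the analysis is descriptive, so no test or error rate is involved; that rates never add, so what fails to add is days and bleed counts; and that the shared day is tiny.

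Finally, ending Treatment the day before the next dose removes the three-day cap for children who continue. A 28-day pause at the boundary would add 24 days, about 14% of 175.5. But overall ABR already counts those days, and so does either phase when a pause falls inside it. Counting them at the boundary treats all pauses alike.

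**Conclusion.** The phase-specific windows are wrong as written at a gap of exactly 3 days and at gaps of 5 days or more; gaps of 1, 2 and 4 days partition cleanly. The overlap day is about 0.6% of the Treatment Phase (1/175.5). The visit-versus-count conflict is a missing statement of precedence; it is the larger effect, at most about 10% of phase length for a child and zero if the visit falls at 50 ED. These percentages assume 3.5-day mean spacing.

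Three stronger readings are tempting and not supported:

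- *That the primary endpoint as a whole is unreliable.* Overall ABR does not use the boundary and is unaffected.
- *That Treatment Phase ABR is the figure for the US post-marketing report.* Protocol 11.3 and SAP 11 include available data for at least 50 ED, and SAP 11 includes all Section 10 summaries, overall ABR among them. No single figure is named.
- *That phase ABR is off by 22%*, from setting 2.31 per bleed at 45 ED (365.25/158) against 1.89 at 55 ED (365.25/193). That contrasts two extremes with the bleed count held fixed. The choice in dispute is visit versus count, and bleeds move with the window, so no systematic bias is shown.

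**What to change.** 1. Use one boundary in SAP 5.1, 10.1 (phase summaries), 10.7.1 and 10.7.2, and keep nominal visits for by-visit tables.
2. For children who continue, end the Treatment Phase window on N − 1, the day before the first dose after the 50th ED, and start Continuation on N. Then T + C − O = 0 at every gap and each bleed falls in one phase.
3. For children who do not continue, keep the last prophylaxis dose plus 3 days, or end of study if earlier.
4. State whether the PK dose counts toward the 50 ED.
5. Define the first Continuation dose identically in 10.7.1 and 10.7.2, with or without the restriction to prophylaxis.

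At minimum, change the cut-back condition in 10.7.1 from N < L + 3 to N ≤ L + 3. That removes the double count but not the omitted days.

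The cost is SAP wording and one derived date per child. No new data are needed, and overall ABR does not change.
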